5 SELECTION AND WITHDRAWAL OF STUDY POPULATION

5.1 Eligibility Criteria

Subjects who satisfy ALL of the following **inclusion** and have NONE of the following **exclusion** criteria may be enrolled in the study:

5.1.1 Inclusion Criteria

1. Male and female subjects ≥ 18 .
2. A clinical diagnosis of mild to moderate facial rosacea.
3. In good general health as determined by a thorough medical history, physical examination, clinical chemistry and hematology.
4. Presence of 3 to 20 inflammatory lesions on the face (i.e. papules/pustules).
5. A Clinician Erythema Assessment (CEA) score of 2-3 at Screening and at Baseline Visits (prior to the investigational product application).
6. Mild to Moderate IGA score of 2-3 at Screening and at Baseline Visits (prior to the investigational product application).
7. Willing to refrain from using any topical or systemic treatments for the treatment of rosacea, other than the investigational product.
8. Females of childbearing potential with a negative urine pregnancy test (UPT) at Screening and Baseline/Day 1 (prior to the investigational product application).

9. Ability to comprehend and comply with study procedures.
10. Agree to commit to participate in the current protocol.
11. Provide written informed consent prior to any study procedure being performed.

5.1.2 Exclusion Criteria

Any subject who meet one or more of the following criteria are excluded from this study.

1. Female subjects who are pregnant, lactating or who are trying to conceive will be excluded from participation in this study.
2. Any uncontrolled chronic or serious disease or medical condition that would normally prevent participation in a clinical trial, or, in the judgment of the Investigator, would put the subject at undue risk, or might confound the study assessments (e.g., other dermatological diseases), or might interfere with the subject's participation in the study, (e.g., planned hospitalization during the study).
3. Particular forms of rosacea (e.g., rosacea conglobata, rosacea fulminans, isolated rhinophyma, isolated pustulosis of the chin, Ocular rosacea Phymatous rosacea, Steroid-induced rosacea, severe rosacea including pyoderma faciale) or other concomitant facial dermatoses that are similar to rosacea such as peri-oral dermatitis, demodicidosis, facial keratosis pilaris, seborrheic dermatitis, acute lupus erythematosus, or actinic telangiectasia.
4. Presence of more than two (2) nodulocystic lesions on the face.
5. Presence of less than 3 and more than 20 inflammatory lesions on the face (i.e. papules/pustules).
6. Severe papulopustular rosacea requiring systemic treatment.
7. Participation at the time of eligibility assessment (Screening) in any other investigational drug or device study or may have participated within 30 days prior to Screening.
8. Commencement of new hormonal therapy or dose change to hormonal therapy within 30 days prior to baseline. Dose and frequency of use of any hormonal therapy started more than 30 days prior to baseline must remain unchanged throughout the study. Hormonal therapies include, but are not limited to, oral, injected or implanted hormonal methods of contraception or placement of an intrauterine device (IUD) or intrauterine system (IUS) or other forms of hormonal contraception that have comparable efficacy (e.g. vaginal ring or transdermal hormone contraception)
9. Presence of beard or excessive facial hair at Screening which would interfere with the study treatments or study assessments and refusal to remove for duration of study.
10. Carcinoid, Pheochromocytoma or other systemic causes of flushing.
11. Known sensitivity to B244 or its components.
12. Refusal to submit to blood and urine sampling for laboratory analysis.
13. Treatment with the following:

Prohibited Topical Treatments:

Topical Treatment	Prohibited Time Frame prior to Baseline
Astringents or abrasives	2 days
RHOFADE™ (oxymetazoline HCl) Cream, 1%	1 week
Bleach baths	1 week
Mirvaso (brimonidine) topical cream	1 week
Vinegar	1 week
Topical Prescription/OTC medications for treatment of acne	2 weeks
Soolantra (Ivermectin 1%) topical cream	1 week
Topical Antibiotic	2 weeks
Use of over the counter antimicrobial	2 weeks
Benzoyl Peroxide	2 weeks
Immunomodulators	4 weeks
Oracea (doxycycline) topical cream	2 weeks
Corticosteroids	4 weeks
Electrocoagulation, Dermabrasion; Facial peels	4 weeks
Dermatologic/surgical procedure on the face	4 weeks
Topical Prescription medications for the treatment of rosacea (e.g. azelaic acid, metronidazole, etc.)	4 weeks
Laser, Phototherapy, Photodynamic Therapy or IPL (intense pulsed light) treatment	4 weeks
Over the counter topical retinoid use on the face	4 weeks

Prohibited Systemic Treatments:

Systemic Treatment	Prohibited Time Frame prior to Baseline
Exposed to excessive ultraviolet (UV) radiation and/or subject was unwilling to refrain from excessive exposure to UV radiation during the course of the study	1 week
Prescription anti inflammatory	2 weeks
Prescription/OTC anti-inflammatory medications (excludes low dose aspirin)	2 weeks
Systemic Antibiotics	4 weeks
Systemic medications for the treatment of rosacea (e.g. doxycycline, tetracycline, macrolides)	4 weeks
Prescription medications for treatment of acne	4 weeks

Corticosteroids (oral or injectable)	4 weeks
Immunomodulators	12 weeks
Oral retinoid use (e.g., isotretinoin), vitamin A supplements greater than 10,000 units/day	6 months

5.2 Study Withdrawal

A subject may voluntarily withdraw from the study at any time and for any reason without prejudice to his or her future medical care. The Investigator, Sponsor, or Medical Monitor may also withdraw a subject at any time if it is medically necessary or in the interest of subject's safety. Additional reasons for premature discontinuation of investigational product may include adverse events and major non-compliance with study procedures, as described below. The withdrawal of a subject from investigational product by the Investigator will be discussed with the Medical Monitor before the subject stops investigational product, whenever possible.

A subject will be discontinued from this study if any of the following criteria are met:

- Withdrawal of consent by the subject is received.
- In the opinion of the Investigator, Medical Monitor or Sponsor, it is not in the subject's best interests to continue in the study.
- Significant non-compliance with study procedures that would interfere with the study results or increase the subject's risks in the study, as determined by the Investigator.
- Development of an intercurrent illness that would jeopardize the safety, or significantly affect assessments of clinical status of a subject.
- Development of any investigational product-related SAE.
- Suspected or laboratory-confirmed pregnancy.

Subjects who discontinued early from the study due to lack of treatment effect after completing at least four weeks of treatment (Day 28) will be included in the mITT and PP population as treatment failures and the change in IGA and CEA from the baseline visit to the last completed visit prior to discontinuation due to lack of efficacy will be carried forward in the primary endpoint analysis. Subjects discontinued early for other reasons will be excluded from the PP population.

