14.1 Subject Population/Data Sets to Be Evaluated

The subject populations are defined as follows:

- **Safety Population:** The safety population includes all randomized subjects who received investigational product.
- **Modified Intent-to-Treat (mITT) Population:** A modified intent-to-treat population includes all subjects who are randomized, applied at least one dose of assigned product, and returned for at least one post-baseline evaluation visit.
- **Per Protocol (PP) Population:** The PP population includes all randomized subjects who met all inclusion/exclusion criteria, were compliant with the assigned study treatment, returned to the study site for the primary endpoint visit within the specified window (± 2 days) OR discontinued from the study as a treatment failure, and did not have any major protocol violations. Subjects who administered at least 50 % of IP, have at least one baseline and post baseline in clinic visit and did not have any major protocol violations.

Subjects who discontinued early from the study due to lack of treatment effect after completing at least eight weeks of treatment should be included in the mITT and PP population as treatment

failures and the change in IGA and CEA from the baseline visit to the last completed visit prior to discontinuation due to lack of efficacy should be carried forward in the primary endpoint analysis. Subjects discontinued early for other reasons should be excluded from the PP population, but included in the mITT population.

The results in the mITT population will be considered definitive for superiority of each active treatment to vehicle with those in the PP population considered supportive. Safety analyses will be performed using the Safety population.

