6.5.4 Per-Protocol (PP) Population

The PP population includes all randomized subjects who met all inclusion/exclusion criteria, were compliant with the assigned study treatment, returned to the study site for the primary endpoint visit within the specified window (± 2 days) OR discontinued from the study as a treatment failure, and did not have any major protocol violations.

Subjects who administered at least 50 % of IP, have at least one baseline and post baseline in clinic visit and did not have any major protocol violations.

Subjects who discontinued early from the study due to lack of treatment effect after completing at least eight weeks of treatment should be included in the mITT and PP population as treatment failures and the change in IGA and CEA from the baseline visit to the last completed visit prior to discontinuation due to lack of efficacy should be carried forward in the primary endpoint analysis. Subjects discontinued early for other reasons should be excluded from the PP population but included in the mITT population.

The results in the mITT population will be considered definitive for superiority of each active treatment to vehicle with those in the PP population considered supportive. Safety analyses will be performed using the Safety population.

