6.7.4 Handling of Missing Data & Sensitivity Analysis

For the primary and secondary analysis no missing values will be imputed. A sensitivity analysis will be performed by Multiple Imputation Regression Analysis using the following factors: treatment, age, gender, race, baseline IGA, baseline CEA, baseline PSA, smokers/non-smokers and the results of the same variable from previous visits.

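### Ending study follow-up for significant non-compliance leaves removed subjects without a Week 8 score, so the definitive mITT superiority test becomes a complete-case analysis

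*Protocol*

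**What the plan says.** Protocol 5.2 introduces its list with "A subject will be discontinued from this study if any of the following criteria are met". One item is "Significant non-compliance with study procedures that would interfere with the study results"; the same item also covers non-compliance that raises the subject's risk, and leaves the decision to the Investigator. SAP version 2.0, section 4.4, repeats both.

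Protocol 5.2 and 14.1, and SAP 4.4 and 6.5.4, carry the last IGA and CEA change forward only for subjects who leave for lack of effect. For everyone else who leaves early, Protocol 14.1 says: "Subjects discontinued early for other reasons should be excluded from the PP population, but included in the mITT population". SAP 6.5.4 agrees and ranks the populations: "The results in the mITT population will be considered definitive for superiority".

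On missing data, SAP 6.7.4 says: "For the primary and secondary analysis no missing values will be imputed". Protocol 14.3.4 has the same rule. Both plan multiple imputation as a sensitivity analysis. SAP 8.3 tests superiority at Week 8 with a continuity-corrected Z-test on proportions, and calls all efficacy endpoints exploratory.

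**The concern.** Non-compliance arises after randomisation and may be related to arm, for instance through irritation, inconvenience or lack of benefit. The PP population already exists to set non-compliant subjects aside. Ending their follow-up goes further, because the Week 8 score is then never collected for any population. If removal differs between arms and is related to outcome, the comparison in the population called definitive is no longer the randomised one.

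The ground at issue protects the data. The same item has a separate ground about risk to the subject, which this point leaves alone.

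**Working it through.** **Following one subject through the rules.** Take a subject removed for significant non-compliance at Week 4.

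- *Membership.* The subject had a dose and a post-baseline visit, so belongs to mITT (SAP 6.5.3) and not to PP (SAP 6.5.4).
- *Week 8 score.* None is scheduled after removal.
- *Carry-forward.* Does not apply, since the reason is not lack of effect.
- *Imputation.* None in the main analysis.
- *Early Termination visit.* Protocol 10.2.9 asks for one, with IGA and CEA. No rule maps it to Week 8, and SAP 7.9 tabulates data by the visit recorded on the CRF. SAP 8.3 equates end of treatment with Week 8, while the Table 14.2.6.1 and 14.2.8.1 shells say only end of treatment. Even if used, the score describes the time of removal.
- *Multiple imputation.* The listed tables, 14.2.10.1 to 14.2.10.3, cover change scores for IGA, CEA and PSA. None covers treatment success.

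So the subject counts in mITT but contributes nothing to the Week 8 success test. A subject removed after Week 8 is unaffected.

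**The plan's own figure.** 104 / (1 − 0.20) = 130, or 65 randomised and 52 completing per arm (Protocol 4.2, 14.2). This reproduces. The plan gives no share of the 20% dropout for removal on this ground, so the splits below are assumptions.

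**Illustration.** Assume 65 randomised per arm, the same true success rate p in both arms, and removed subjects all non-responders. With a share r removed:

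- completer success rate = p / (1 − r)
- evaluable n = 65 × (1 − r), rounded: 58 at 10%, 62 at 5%, 55 at 15%, 52 at 20%

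For p = 20% and removal of 20% on B244 and 5% on vehicle: 0.20/0.80 = 25.0% against 0.20/0.95 = 21.1%, a spurious 3.9 points. For p = 10%: 0.10/0.80 = 12.5% against 0.10/0.95 = 10.5%, or 2.0 points.

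Exact binomial enumeration of the pooled Z-test with correction ½(1/n₁ + 1/n₂), two-sided 5%, counting only results that favour B244 (nominal 2.5%):

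| Removed, B244 / vehicle | Completers, p = 20% | False superiority | Completers, p = 10% | False superiority |
|---|---|---|---|---|
| 0 / 0 | 20.0% v 20.0% | 1.5% | 10.0% v 10.0% | 1.2% |
| 10 / 5 | 22.2% v 21.1% | 2.1% | 11.1% v 10.5% | 1.5% |
| 15 / 5 | 23.5% v 21.1% | 3.1% | 11.8% v 10.5% | 2.1% |
| 20 / 5 | 25.0% v 21.1% | 4.6% | 12.5% v 10.5% | 2.7% |

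The 10% is the vehicle rate in Protocol 14.2. The 20% is an assumption. With 20% removed from both arms the spurious difference is 0, and false superiority is 1.4% (p = 20%) or 1.1% (p = 10%). By symmetry, 5% removed on B244 and 20% on vehicle gives the same probabilities in favour of vehicle.

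The code line in SAP 8.3 shows no correction option, although the text names the corrected test. Without correction, the four values at p = 20% are 2.4%, 3.7%, 4.9% and 7.2%.

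**Power is not the issue.** Suppose 33% and 10% hold among completers. Then 52 per arm gives 76.3% exact power with the corrected test. Keeping all 65 with missing as non-response gives 0.8 × 33% = 26.4% against 0.8 × 10% = 8.0%, and 75.2%.

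**The case against.** A reader might infer that the mITT test is a per-protocol analysis in all but name. The documents do not support that. mITT has no compliance, eligibility, visit-window or major-violation condition. PP has all of these, with a threshold of half the product, and the shell for Table 14.1.1.3 lists failure of that threshold as its own reason, apart from withdrawal.

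Nor does the rule remove every non-compliant subject. It covers significant non-compliance only. Protocol 11.2.6.1 has missed applications clarified and documented, and Protocol 8.2 leaves prohibited treatments to a written decision by the Medical Monitor or sponsor. Less compliant subjects who attend Week 8 stay in the mITT test.

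The plan also has partial safeguards: explicit mITT membership, the Early Termination scores and multiple imputation. They count, but none supplies a Week 8 success value in the main test.

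Investigators are blinded, so removal related to arm is a risk and not a certainty. The bottles are identical, but Protocol 6.2 describes B244 as cloudy light pink and vehicle as clear and colourless. The illustration runs in one direction and assumes that all removed subjects are non-responders. At the 10% rate with the corrected test, only the widest split passes 2.5%, and barely. Finally, efficacy is exploratory and the primary objective is safety. All of this limits the size of the problem.

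It could be said that an SAP rule for early leavers is enough. Such a rule is needed, but it cannot restore a Week 8 score that the protocol stopped the site from collecting.

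**Conclusion.** The point holds as one about complete-case handling. A stated rule, applied after randomisation on the Investigator's judgement, ends data collection for some subjects, and nothing in the main analysis replaces their Week 8 score.

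The size depends on assumptions the documents cannot settle: how many are removed on this ground before Week 8, how unequally, and with what outcomes. In the scenarios shown, false superiority reaches at most 4.6% at an assumed 20% success rate and 2.7% at the planned 10% vehicle rate, against 1.5% and 1.2% with everyone followed. Equal removal gives no spurious difference, and more removal on vehicle biases against B244. Because efficacy is exploratory, this should be changed but does not undermine the trial's primary objective.

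**What to change.** - In Protocol 5.2 and SAP 4.4, remove interference with study results as a ground for ending study follow-up. Leave the risk and safety grounds as they are.
- Reconcile the two ideas in that section: its opening paragraph treats major non-compliance as a reason for stopping product and points to the text below, but the list below ends participation in the study.
- State that a non-compliant subject who has not withdrawn consent continues the scheduled assessments through Week 12, is analysed in mITT with the observed Week 8 score, and is set aside only in PP.
- In the SAP, state whether and how Early Termination scores enter the Week 8 success test. Reconcile the carry-forward rule with the no-imputation rule, and its two thresholds: four weeks in Protocol 5.2 and SAP 4.4, eight in Protocol 14.1 and SAP 6.5.4.
- Add a non-compliance row to the disposition shells, Tables 14.1.1.1 and 14.1.1.2, which have none, so that the number removed is visible.

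Nothing here concerns whether product use continues. The cost is protocol and SAP wording, a few subjects attending visits already scheduled, and possibly a slightly diluted mITT estimate.

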10.2.9 Early Termination Visit

Every attempt should be made to complete all visits during the defined window periods. Subjects who do not complete all required study visits and withdraw from the study before Week 12 final visit, will be asked to complete the Early Termination Visit.

During the visit, the following will be obtained:

- Concomitant and Prohibited Therapies review
- Physical Exam
- Collection of Vital Signs
- Urine Pregnancy Test for WOCBP
- Venipuncture for Laboratory Assessment & Urinalysis
- Blood for biomarkers
- Investigator's Global Assessment [IGA]
- Clinician's Erythema Assessment [CEA]
- Skindex 16
- Patient Self-Assessment (PSA)
- Telangiectasia Evaluation
- IP collection
- IP compliance
- Study cleanser and moisturizer collection
- Study diary
- Adverse event collection and assessment

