Disposition	B244 Topical Spray n (%)	Placebo n (%)	All Patients n (%)
Randomized	xx (xx.x)	xx (xx.x)	xx (xx.x)
Treated	xx (xx.x)	xx (xx.x)	xx (xx.x)
Completed	xx (xx.x)	xx (xx.x)	xx (xx.x)
Completed Week 1	xx (xx.x)	xx (xx.x)	xx (xx.x)
Completed Week 4	xx (xx.x)	xx (xx.x)	xx (xx.x)
Completed Week 8	xx (xx.x)	xx (xx.x)	xx (xx.x)
Completed Week 12	xx (xx.x)	xx (xx.x)	xx (xx.x)
Discontinued	xx (xx.x)	xx (xx.x)	xx (xx.x)
Withdrawal of consent	xx (xx.x)	xx (xx.x)	xx (xx.x)
In the opinion of the Investigator, it is not in the subject's best interests to continue in the study	xx (xx.x)	xx (xx.x)	xx (xx.x)
Pregnancy	xx (xx.x)	xx (xx.x)	xx (xx.x)
Occurrence of an Adverse Event (AE) or Serious Adverse Event (SAE), which, in the opinion of the Investigator warrants discontinuation of the subject from the study	xx (xx.x)	xx (xx.x)	xx (xx.x)
The subject is lost to follow-up	xx (xx.x)	xx (xx.x)	xx (xx.x)
Other	xx (xx.x)	xx (xx.x)	xx (xx.x)

NOTE: The percentages are based on the number of Randomized subjects.

Subjects may have more than one reason for discontinuation, and they are counted more than once.

Snapshot Data DD-MMM-YYYY

Source: <Dataset>

Program Name: <Pgm name>

Table 14.1.1.3
 Analysis Population and Exclusions
 All Subjects

Number of Subjects	B244 Topical Spray n (%)	Placebo n (%)	All Patients n (%)
Enrolled	xx	xx	xx
Randomized	xx	xx	xx
Included in Safety Population	xx	xx	xx (xx.x%)
Reasons for Exclusion from Safety Population			
	xx	xx	xx (xx.x%)
	xx	xx	xx (xx.x%)
Included in Full Analysis Set	xx	xx	xx (xx.x%)
Reasons for Exclusion from Safety Population			
	xx	xx	xx (xx.x%)
Included in Per Protocol Population	xx	xx	xx (xx.x%)
Reasons for Exclusion from Per Protocol Population			
Lost To Follow Up	xx	xx	xx (xx.x%)
Major Deviation	xx	xx	xx (xx.x%)
Not 50% Ip Compliant	xx	xx	xx (xx.x%)
Screen Failure	xx	xx	xx (xx.x%)
Withdrawal of Consent By Subject	xx	xx	xx (xx.x%)

NOTE: The percentages are based on the number of All subjects.

Snapshot Data DD-MMM-YYYY

Program Name: <Pgm name>

Source: <Dataset>

Table 14.1.2.1
 Summary of Protocol Deviations (PD)/Violations (PV)
 mITT Population

Deviation/Violation Description of Violation/deviation	Deviation/Violation Category “Major” or “Minor”	B244 Topical	Placebo	All
		Spray n (%) xx	n (%) xx	Patients n (%) xx

NOTE: The percentages are based on the number of ITT Population.

Source: <Dataset>

Snapshot Data DD-MMM-YYYY
 Program Name: <Pgm name>

Repeat for Safety Population

Table 14.1.3.1

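### The per-protocol rules contradict each other for subjects who leave between Week 8 and Week 12; read literally, the exclusion rule makes the Week 8 per-protocol result depend on an event after the endpoint

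*Protocol*

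**What the plan says.** **Exclusion rule.** Protocol 5.2: "Subjects discontinued early for other reasons will be excluded from the PP population". SAP v2.0 section 4.4 carries the same sentence. Protocol 14.1 has "Subjects discontinued early for other reasons should be excluded from the PP population, but included in the mITT population", and SAP v2.0 section 6.5.4 matches it. None of the four places limits the rule in time.

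**Entry rule.** The main PP sentence in Protocol 14.1 and SAP 6.5.4 admits subjects who met the eligibility criteria, complied with treatment, had no major violation and "returned to the study site for the primary endpoint visit within the specified window". Discontinuing as a treatment failure is the alternative to attending that visit. The visit is not named.

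**Timing.** Product stops at Week 8, and an off-treatment visit follows at Week 12 (Protocol 4.1). SAP 8.3 tests superiority at Week 8. Protocol 10.2.9 says that subjects who miss required visits and "withdraw from the study before Week 12 final visit, will be asked to complete the Early Termination Visit".

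**Table shell.** SAP v2.0 Table 14.1.1.3 lists loss to follow-up and "Withdrawal of Consent By Subject" among the reasons for exclusion from PP, without reference to time.

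**Role.** mITT is definitive for superiority and PP is supportive. All efficacy endpoints are exploratory, and the primary objective is safety.

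**The concern.** A subject can take eight weeks of product, attend Week 8 in window, and then withdraw consent or be lost before Week 12. That subject satisfies the entry rule and is also caught by the exclusion rule. The plan gives no order of precedence, so the programmer has to choose.

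If the exclusion wins, membership of the Week 8 PP set depends on something that happens after the Week 8 outcome is recorded and that the outcome may influence. A subject who has cleared may see no reason to return, and so may one who is disappointed. The handling is also uneven: leaving in those four weeks for lack of effect keeps a subject in PP as a treatment failure, while leaving for any other reason removes the subject. At stake is the meaning of the PP tables planned for the IGA and CEA success endpoints, and whether the choice is made before or after treatment codes are known.

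**Working it through.** **1. Does early discontinuation extend past Week 8?** Three texts bear on this.

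- Protocol 10.2.9 places the cut-off for an early termination visit at Week 12.
- Protocol 14.1 speaks of "Subjects who discontinued early from the study due to lack of treatment effect after completing at least eight weeks of treatment". Treatment lasts eight weeks, so that phrase covers people who leave after treatment is complete.
- No section states an earlier cut-off for PP membership.

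The literal reading of the exclusion therefore includes Weeks 8 to 12.

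**2. The rules applied to a compliant, eligible subject with an in-window Week 8 visit who leaves at Week 10.**

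| Reason for leaving | Main PP sentence | Exclusion / carve-out sentences |
|---|---|---|
| Lack of effect | In | In, as treatment failure (meets the four-week and the eight-week condition) |
| Any other reason | In | Out |

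The conflict is confined to the second row. It assumes that the primary endpoint visit is Week 8, which is inferred from SAP 8.3.

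**3. The plan's own figure.** Protocol 4.2 gives 130 enrolled, 20% dropout and 104 as the planned sample size. 104 / (1 − 0.20) = 130, which reproduces. Expected dropouts are 130 × 0.20 = 26.

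**4. How many could be affected?** The documents do not say how the 26 divide around Week 8. Assume that the 20% runs to Week 12, that all leave for reasons other than lack of effect, and that a share f leaves after a valid Week 8 visit. The number in conflict is 26 × f:

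| f | Subjects in conflict | PP ceiling if excluded | PP ceiling if kept |
|---|---|---|---|
| 0 | 0 | 104 | 104 |
| 10% | 2.6 | 104 | about 107 |
| 25% | 6.5 | 104 | about 110 |
| 50% | 13 | 104 | 117 |
| 100% | 26 | 104 | 130 |

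Two simple timing assumptions give a middle value:

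- Even spread over 84 days: 130 × 0.20 × 28/84 = 8.7.
- Constant hazard: 130 × (0.8^(56/84) − 0.8) = 130 × (0.8618 − 0.8) = 8.0.

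That is about 8 to 9 subjects, or roughly 4 per arm: about 56 per arm with Week 8 data against 52 after exclusion.

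**5. How far could the estimate move?** Use the planning rates of 33% and 10% (Protocol 14.2). With 56 per arm the expected responders are 18.48 and 5.6, a difference of 23 points. Remove 4 per arm:

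- Responders in both arms: (14.48 − 1.6)/52 = 24.8 points.
- Non-responders in both arms: (18.48 − 5.6)/52 = 24.8 points.
- Active responders and vehicle non-responders: (14.48 − 5.6)/52 = 17.1 points.
- Active non-responders and vehicle responders: (18.48 − 1.6)/52 = 32.5 points.

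Selection in the same direction in both arms moves 23 to about 25. Only opposite selection in the two arms reaches 17 or 32.

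**The case against.** The best defence is contextual. The main PP sentence sets discontinuation as a treatment failure against attending the endpoint visit, which suggests leaving before it. In Protocol 5.2 the exclusion follows a carry-forward rule, and carry-forward is needed only when the endpoint value is missing. Section 10.2.9 says who is asked to attend a visit and does not define PP membership. Table 14.1.1.3 is a shell of labels: it lists screen failure as a PP exclusion and omits adverse events and pregnancy, so it is weak evidence of a rule.

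Much of this stands. A reader might infer that the plan simply drops subjects with a valid Week 8 result. The documents do not support that, because the entry sentence in the same sections keeps them. They support a contradiction. The defence does not remove it, since the eight-week wording in Protocol 14.1 and SAP 6.5.4 applies early discontinuation to people who have finished treatment. That wording itself conflicts with the four-week condition in Protocol 5.2 and SAP 4.4, so it is not decisive in the other direction.

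A reader might also take 17 to 32 points as the likely bias. It is a worst case. The 32 needs 4 of the 5.6 expected vehicle responders to leave (71%) and no vehicle non-responder.

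A loss of power is also tempting to claim. The uncorrected Z-test gives 87% at 56 per arm against 84% at 52, but SAP 8.3 names a continuity-corrected test, for which enumeration gives about 81–82% against 76–78% depending on the variance form. The plan attaches no power claim to PP, so neither pair measures a failure of the design.

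**Conclusion.** The point holds as an internal contradiction in the PP definition, with a selection problem if the exclusion sentence is applied as written. The number of subjects is not derivable from the documents. The range of 0 to 26 and the middle value of 8 to 9 both assume that the 20% dropout is counted to Week 12. They also assume that late leavers were otherwise PP-eligible and left for reasons other than lack of effect. The plan does not define completion; if the 20% means loss before the Week 8 endpoint, the 8 to 9 figure has no basis. If nobody leaves after Week 8, the effect is zero.

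The reach is limited. mITT is definitive and retains these subjects, as "Subjects discontinued early for other reasons should be excluded from the PP population but included in the mITT population" confirms, so the definitive analysis loses no Week 8 data. PP is supportive, efficacy is exploratory, and the safety objective is unaffected. The correction is still worth making because it is specific, needs no data, and is credible only if settled while the trial is blinded.

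**What to change.** Before unblinding, revise SAP 4.4 and 6.5.4 to state that subjects who discontinue before the Week 8 visit for reasons other than lack of treatment effect are excluded from PP, and that discontinuation after a completed, in-window Week 8 visit does not affect PP membership. Name Week 8 as the primary endpoint visit. In Table 14.1.1.3, restrict the loss-to-follow-up and consent-withdrawal rows to the time before Week 8. In the same revision, reconcile the lack-of-effect condition, which is four weeks in Protocol 5.2 and SAP 4.4 but eight weeks in Protocol 14.1 and SAP 6.5.4.

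The SAP part costs a short text revision and two row labels, with no new data collection. Protocol 5.2 and 14.1 should be aligned at the next amendment. Protocol section 19 requires sponsor agreement and IRB approval for that, so it is more than a one-sentence edit.
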